9.2.10 Imaging test (thoracoabdominal-pelvic CT/MRI)

Imaging test will be performed within 4 weeks (28 days) prior to enrollment (including the same day of week as the day of enrollment). The results of imaging diagnosis/test performed before obtaining consent may be used if it is performed within 4 weeks (28 days) prior to enrollment.

Furthermore, the data of measurable lesion should be evaluated with imaging test conducted within 2 weeks (14 days) prior to initiation of protocol treatment (including the same day of week as the day of enrollment) preferably. If another imaging test has been conducted newly after enrollment but before initial administration, this data should be recorded in CRF.

After initiation of protocol treatment, imaging test will be performed every 8 weeks (56 days) with protocol treatment initiation date (Day 1) of Course 1 as the starting point. However, when 1 year has passed since initiation of protocol treatment, imaging may be performed once every 12 weeks (84 days), counting from the point in time at which 1 year has passed. (For details, see “Table 9.a Study calendar (phase I part of the study)” or “Table 9.b Study calendar (phase II part of the study).”

Thoracoabdominal-pelvic CT (in principle, contrast CT; a slice width of 5 mm or less is recommended, but MRI is also acceptable) will be used for imaging test, and the modality and the date of imaging test will be entered into the CRF. If necessary, brain MRI / CT and a neck CT will be performed.

In principal, the same modality should be used for imaging test during protocol treatment throughout the study period.

The investigator or the subinvestigator should evaluate the test results according to the RECIST v1.1 (see Appendix A) and enter the determined results into the CRF.

Furthermore, for subjects withdrawn from the study for any reason other than imaging test results such as clinical PD, imaging test specified at the time of discontinuation should be performed within 4 weeks (28 days) including the day of decision (including the same day of week as the day of decision).

If the subject is not determined to have PD on imaging up to the time of withdrawal, the following information should be collected until the subject dies or the sponsor terminates the study, even after follow-up treatment has been started.

- Day of decision on clinical PD (only when the subject is not determined to have clinical PD by the time of discontinuation)

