4.1 Handling of cases/data

(1) Handling of laboratory values/subjective and objective findings of adverse events

Adverse events recorded on the adverse event form will be coded using Medical Dictionary for Regulatory Activities (MedDRA) (ver.21.0) and summarized by system organ class (SOC) and preferred terms (PTs). Skin disorders will be regarded as events classified into “Skin and subcutaneous tissue disorders” of SOC or “Paronychia” by PT. The PTs classified as skin toxicity (Rash acneiform, Paronychia, Dry skin, Pruritus) are defined in Table 4.1.

Table 4.1 Events classified as skin toxicity

Rash acneiform	Acne, Dermatitis acneiform, Folliculitis, Rash, Dermatitis, Drug eruption, Rash pruritic, Eczema, Skin disorder, Rash generalized, Seborrhoeic dermatitis
Paronychia	Paronychia, Nail avulsion, Onychoclasia, Onychomadesis, Nail disorder, Ingrowing nail, Excessive granulation tissue, Pyogenic granuloma
Dry skin	Dry skin, Skin fissures, Xeroderma, Skin exfoliation, Skin chapped, Eczema asteatotic, Hyperkeratosis
Pruritus	Pruritus, General pruritus

(2) Handling of adverse event grade

If an AE is assessed multiple times in the same subject, the highest grade among all AE assessments shall be reported as the worst grade of the AE.

(3) Handling of missing/ejected data

Missing data will not be complemented unless the details of individual analysis items are specified. When rejecting data, the corresponding data will be indicated and the reason for rejection clarified in a table. However, handling of patients with no occurrence of events related to Progression-Free Survival (PFS), Overall Survival (OS), or Time to Treatment Failure (TTF) will be described in each section.

(4) Protocol treatment and acceptable range for tests

Performed items	Protocol specification	Allowance range
Protocol treatment	From the date of treatment of the previous course (Day 1) to after 4 weeks (Day 29)	Scheduled day \pm 3 days

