7.2.4.2 Secondary endpoints and analysis method

[Secondary endpoints]

1) Progression-free survival (PFS)

PFS is the period from the day of enrollment until the day of documented PD (radiological decision or clinical decision) or the day of death due to any cause, whichever comes earlier.

For surviving subjects without documented progression, the period will be cut off on the final day on which progression-free status is confirmed (final day of progression-free survival confirmation). Events and the cut-off will also be handled the same way in subjects who have discontinued protocol treatment for reasons such as toxicity and refusal of treatment, even if another (follow-up) therapy is added. Thus, the time of treatment discontinuation or the day of follow-up treatment initiation will not be the cut-off.

[Analysis method]

Kaplan-Meier method will be used to illustrate survival curve until the onset of event in the “full analysis set,” and the point estimation value of survival rate and its 95% confidence interval (two-sided) will be calculated at the quartile of PFS and specified time points. The

Log-Log conversion of Brookmeyer and Crowley will be used to calculate the 95% confidence intervals of the quartiles for PFS.

2) Overall survival (OS)

OS is the period from the day of enrollment until death by any cause. For surviving subjects, the period is terminated on the final day of survival confirmation or data cut-off date, whichever occurs earlier.

[Analysis method]

Kaplan-Meier method will be used to illustrate survival curve until the onset of event in the “full analysis set,” and the point estimation value of survival rate and its 95% confidence interval (two-sided) will be calculated at the quartile of OS and specified time points. The Log-Log conversion of Brookmeyer and Crowley will be used to calculate the 95% confidence intervals of the quartiles for OS.

3) Response rate (RR)

RR is the percentage of subjects whose best overall response after enrollment according to RECIST ver. 1.1 is either complete response or partial response. Overall response will be graded by favorability in the order of complete response (CR), partial response (PR), stable disease (SD), progressive disease (PD), and not evaluable (NE). Best overall response is the best response recorded throughout all courses.

[Analysis method]

RR of target lesion and its 95% confidence interval (two-sided) will be calculated in the “full analysis set.”

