Further, the maximum tumor reduction rate will be calculated for each subject, and a waterfall plot will be created by arranging the maximum tumor reduction rate in ascending order. Lines of reference at -30% indicating PR and at + 20% indicating PD will be drawn.

$$\text{Reduction ratio of SoD} = \frac{\text{SoD at evaluation point} - \text{SoD before treatment}}{\text{SoD before treatment}} \times 100\%$$

4) Duration of response (DOR)

DOOR is the period from the day when either CR or PR is first confirmed until the day of documented PD or the day of death due to any cause, whichever occurs earlier. For surviving subjects without documented PD, the period will be cut off on the final day of progression-free survival confirmation.

[Analysis method]

The Kaplan-Meier survival curve will show the subject status until the onset of event for the subjects who showed response among the “full analysis set,” and the point estimation value of survival rate and its 95% confidence interval (two-sided) will be calculated at the quartile of DOOR and specified time points.

5) Disease control rate (DCR)

DCR is the percentage of subjects whose best overall response after enrollment according to RECIST ver. 1.1 is CR, PR, or SD.

[Analysis method]

DCR and its 95% confidence interval (two-sided) will be calculated in the “full analysis set.”

6) Time to treatment failure (TTF)

TTF is the period from the day of enrollment until the day of the decision to discontinue protocol treatment, the day of documented progression during protocol treatment (day of decision on clinical PD or radiological PD), or the day of death due to any cause, whichever comes earlier. Subjects not included in the above criteria will be censored at the dose starting date in the final course.

[Analysis method]

Kaplan-Meier method will be used to illustrate survival curve until the onset of event in the “full analysis set,” and the point estimation value of survival rate and its 95% confidence interval (two-sided) will be calculated at the quartile of TTF and specified time points. The Log-Log conversion of Brookmeyer and Crowley will be used to calculate the 95% confidence intervals of the quartiles for TTF.

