7.2.4.3 Subgroup analysis of efficacy

1) Subgroup analysis on the following items will be performed for each background factor described below. The same analysis method will be used as in Sections 7.2.4.1 and 7.2.4.2. Using all background factors as explanatory variables, multivariate analysis will be performed using the Cox proportional hazard model for PFS, OS, and TIF. Similarly, using all background factors as explanatory variables, logistic regression analysis will be performed for PFS rate and DCR.

7.2.4.3.1.1 PFS rate

7.2.4.3.1.2 PFS

7.2.4.3.1.3 OS

7.2.4.3.1.4 RR

7.2.4.3.1.5 DCR

7.2.4.3.1.6 TTF

Background factors:

Age (≥ 20 years < 65 years, ≥ 65 years < 75 years), sex, ECOG Performance status (P.S.) [before dosing on Day 1 of Course 1 (0, 1)], information on primary tumor location [right, left], adjuvant chemotherapy (yes, no), resection of primary lesion (yes, no), number of days since the start of first-line treatment (< 600 days, ≥ 600 days)

2) A landmark analysis for PFS, OS, and TIF will be performed for each landmark point after enrollment. Patients developing applicable events by the landmark point after enrollment and those who have been discontinued will be excluded from the analysis. The same analysis method will be used as in Section 7.2.4.2.

7.2.4.3.2.1 PFS

7.2.4.3.2.2 OS

7.2.4.3.2.3 TTF

Factor	Landmark point	Category
Skin Toxicity,	Week 6	$\leq G1, \geq G2$
Skin Toxicityr	Week 10	$\leq G1, \geq G2$

Factor	Landmark point	Category
Stomatitis	Week 6	$\leq G1, \geq G2$
Stomatitis	Week 10	$\leq G1, \geq G2$
Neutropenia	Week 6	$\leq G0, \geq G1$
Neutropenia	Week 6	$\leq G2, \geq G3$
Early Tumor Shrinkage (ETS)*	Week 8	Yes, No

*ETS refers to the case of tumor shrinkage by at least 20% within 8 weeks after enrollment.

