7.2.4.4 Other efficacy analysis items

1) ETS

The presence/absence of cases with tumor shrinkage by at least 20% within 8 weeks after enrollment, the number of patients who dropped out (discontinued protocol treatment) within 8 weeks after enrollment in the full analysis set, and the dropout rate will be shown.

2) Administration of each drug and the change from the onset of response to death or completion of observation

Swimmers plot will be created to illustrate the change from the onset of response to death or completion of observation.

Date of response onset: the date CR or PR is first confirmed

Vertical axis: case

Horizontal axis: duration (days)

Administration status: A bar graph showing the duration of TAS administration (from Day 1 of TAS-102 to the date of last administration of TAS-102, with “x” indicating administration of panitumumab.

▲ will indicate the date of discontinuation of protocol treatment.

Therapeutic effect: ○ will indicate the date of response onset

■ will indicate the confirmation date of PD.

Survival: The OS part after discontinuation of protocol treatment will be indicated as ---- (survivors will be distinguished by color)

Post treatment: ● will indicate the start date of post treatment.

3) Time-course change in the reduction rate of the sum of target lesion diameters

A spider plot will be created to describe the reduction rate of the sum of target lesion diameters in all patients by best overall response of PR, SD, and PD.

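### Early tumor shrinkage is cut off at day 56 from enrollment with no window, but compliant first scans fall on days 49 to 77, and the SAP does not say how subjects without a scan by day 56 are classified

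*SAP*

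**What the plan says.** SAP v4.0 section 7.2.4.3, part 2, plans landmark analyses of PFS, OS and TTF. One factor is early tumor shrinkage (ETS), with a Week 8 landmark and the categories Yes and No. The footnote reads "ETS refers to the case of tumor shrinkage by at least 20% within 8 weeks after enrollment". Section 7.2.4.4, item 1, uses the same limit for a descriptive summary: "The presence/absence of cases with tumor shrinkage by at least 20% within 8 weeks after enrollment", together with the number and rate of dropouts in that period.

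The landmark exclusion rule is "Patients developing applicable events by the landmark point after enrollment and those who have been discontinued will be excluded from the analysis". It does not mention subjects who are on treatment and event-free but not yet scanned. The general rule in SAP 4.1 (3) is "Missing data will not be complemented unless the details of individual analysis items are specified".

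Scans follow a different clock. Protocol 9.2.10 says "imaging test will be performed every 8 weeks (56 days) with protocol treatment initiation date (Day 1) of Course 1 as the starting point". Table 9.c allows 7 days either side in the first year. Protocol 8.1 and 7.3.1 (item 4) have treatment start in principle within 14 days of registration, and 7.3.1 foresees later starts. PFS, OS and TTF are all counted from enrollment (SAP 7.2.4.2); for example, "OS is the period from the day of enrollment until death by any cause".

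**The concern.** The cut-off and the scan that supplies the measurement have different starting points, and nothing bridges them. A subject who starts treatment 10 days after registration and is scanned exactly on schedule is scanned on day 66. Shrinkage seen on that scan cannot count as ETS.

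The primary endpoint also runs from enrollment, but there the plan gives a window of 2 weeks either side and says how subjects without imaging are counted (Protocol 13.3.3.1, SAP 7.2.4.1). ETS has neither. The acceptable-range table in SAP 4.1 (4) covers protocol treatment, not imaging.

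At stake are the ETS rate in 7.2.4.4 and the Yes/No curves in 7.2.4.3. Both would depend partly on the delay between registration and treatment, and on a classification choice that the SAP leaves open.

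**Working it through.** The plan gives no figure of its own for this point, so the check is date arithmetic.

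**Inputs.** Cut-off: 8 × 7 = day 56 from enrollment (SAP 7.2.4.3, 7.2.4.4). Scan due: 56 days from Course 1 Day 1 (Protocol 9.2.10). Deviation v: −7 to +7 days (Table 9.c). Lag d from enrollment to treatment: 0 to 14 days (Protocol 7.3.1, 8.1).

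**Formula.** First-scan day from enrollment = 56 + d + v. The scan qualifies if d + v ≤ 0.

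- Earliest compliant scan: 56 + 0 − 7 = day 49. Latest: 56 + 14 + 7 = day 77.
- A due-date scan (v = 0) qualifies only if d = 0.
- With d from 1 to 7, the scan must be at least d days early.
- With d from 8 to 14, the earliest compliant scan is on days 57 to 63, so none qualifies.

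**Share qualifying (q).** The documents give no distribution of lags or scan dates, so these are illustrations with equal weights. At lag d from 0 to 7, 8 − d of the 15 allowed scan days qualify.

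- Lag 0–14: (8+7+6+5+4+3+2+1)/(15 × 15) = 36/225 = 16%.
- Lag 0–7: 36/120 = 30%.
- Lag 0–3: 26/60 = 43%.
- Lag 0–3, no late scans (v from −7 to 0): 26/32 = 81%.
- Lag 0, no late scans: 100%.

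**If the others are coded No.** Let p be the true proportion with at least 20% shrinkage at the first scheduled scan, assumed unrelated to scan timing. Displayed ETS rate = p × q. True shrinkers among No = p(1 − q)/(1 − pq). For example, at q = 0.16 and p = 0.30: 0.252/0.952 = 26%.

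**If the others are missing.** Subjects keeping an ETS value = 52 × q, before landmark exclusions. Standard errors grow by about 1/√q.

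| q | Displayed ETS, p = 30% / 50% | Shrinkers among No, p = 30% / 50% | With a value, of 52 | Standard error factor |
|---|---|---|---|---|
| 16% | 5% / 8% | 26% / 46% | 8 | 2.5 |
| 43% | 13% / 22% | 20% / 36% | 23 | 1.5 |
| 81% | 24% / 41% | 7% / 16% | 42 | 1.1 |
| 100% | 30% / 50% | 0% / 0% | 52 | 1.0 |

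**Later cut-offs, uniform lag 0–14.** Day 70 (d + v ≤ 14) covers 197/225 = 88%. Day 77 (d + v ≤ 21) covers 225/225.

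**The case against.** The best defence is that the SAP does not impute missing data. Scoring an unscanned subject as No would assign a value nobody observed. Where the plan wants unassessed subjects counted as failures, as for the primary endpoint, it says so. That carries weight: treating these subjects as missing is closer to SAP 4.1 (3), and on that reading the loss is mainly precision. It does not close the gap, because the factor table offers only Yes and No and the exclusion rule does not remove these subjects. A reader might infer that the SAP directs coding as No; it does not say so.

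A reader might also infer a diluted hazard ratio for ETS. The documents do not support that as a planned result. Part 2 of 7.2.4.3 uses the methods of 7.2.4.2, which are Kaplan-Meier curves, quartiles and survival rates. Cox regression appears only in part 1, for listed background factors that do not include ETS. What can be distorted is the set of curves.

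The consequence is also limited. ETS entered with SAP v4.0 and is not a protocol endpoint. Shrinkage is shown without a day-56 limit in the waterfall plot, the spider plot and the RECIST listing (7.2.4.2, 7.2.4.4 and 7.2.7.11). All this stands. It lowers the importance of the point but does not make the cut-off fit the scan schedule.

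**Conclusion.** The point holds as a defect in an exploratory analysis and should be corrected. The range of days 49 to 77, and the fact that no compliant scan qualifies at lags of 8 to 14 days, follow directly from the documents. How many subjects are affected does not. The 16% is one illustration, and a reader should not take it to mean that 84% of scans will be lost: prompt starts and punctual scans could bring the qualifying share to 100%.

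Applied literally with the Yes/No table, shrinkers first scanned on days 57 to 77 are not counted, so the ETS rate is understated. In the OS curves they are mixed into No, which blurs the contrast. For PFS and TTF the direction is not fixed, because progression found on a first scan after day 56 also counts as an early event, probably in No. If these subjects are treated as missing, the cost is mainly precision. Primary and secondary endpoint estimates are unaffected.

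**What to change.** In both 7.2.4.3 and 7.2.4.4:

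1. Define ETS as a decrease of at least 20% in the sum of diameters at the first scheduled post-baseline scan, 56 ± 7 days from Course 1 Day 1.
2. Report subjects without that scan as not evaluable, with their number.
3. Move the ETS landmark to day 77 (Week 11) after enrollment. This covers every on-schedule scan for lags up to 14 days and leaves the time origin of PFS, OS and TTF unchanged. A scan after day 77 should not supply a value to the landmark analysis. Week 10, already used for other factors, is a weaker option: 88% under the uniform assumption.

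The work is SAP wording and programming. The statistical cost is a smaller landmark set, because subjects who progress at the first scan leave the PFS and TTF sets. They leave the OS set too if discontinuation in the exclusion rule means stopping protocol treatment.

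- Under a smooth exponential curve, 52 × 2^(−w/m), the set falls from 35 at Week 8 to 30 at Week 11 for m = 14.1 weeks (the RAS wild-type panitumumab median in Protocol 6.2.2.2). It falls from 41 to 37 for m = 22.7 weeks, which corresponds to the expected 48% at 24 weeks.
- If progression is assumed to be detected only at scans, simulation puts the loss at 5 to 10 of 52 (non-shrinker median 14.1 weeks, 30–50% shrinking), 3 to 7 (22.7 weeks), or 7 to 14 if those medians apply to all subjects: roughly 3 to 14 overall.

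Two smaller costs remain. Real shrinkage on an off-window scan is not used. For starts later than day 14, coverage falls to 8/15 (53%) at lag 21 and 1/15 (7%) at lag 28.

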7.2.4.4 Other efficacy analysis items

1) ETS

The presence/absence of cases with tumor shrinkage by at least 20% within 8 weeks after enrollment, the number of patients who dropped out (discontinued protocol treatment) within 8 weeks after enrollment in the full analysis set, and the dropout rate will be shown.

2) Administration of each drug and the change from the onset of response to death or completion of observation

Swimmers plot will be created to illustrate the change from the onset of response to death or completion of observation.

Date of response onset: the date CR or PR is first confirmed

Vertical axis: case

Horizontal axis: duration (days)

Administration status: A bar graph showing the duration of TAS administration (from Day 1 of TAS-102 to the date of last administration of TAS-102, with “x” indicating administration of panitumumab.

▲ will indicate the date of discontinuation of protocol treatment.

Therapeutic effect: ○ will indicate the date of response onset

■ will indicate the confirmation date of PD.

Survival: The OS part after discontinuation of protocol treatment will be indicated as ---- (survivors will be distinguished by color)

Post treatment: ● will indicate the start date of post treatment.

3) Time-course change in the reduction rate of the sum of target lesion diameters

A spider plot will be created to describe the reduction rate of the sum of target lesion diameters in all patients by best overall response of PR, SD, and PD.

7.2.4.5 Level of significance, confidence coefficient

Significance level: Main analysis only, 5% (one-sided); other analyses, 5% (two-sided)

Confidence coefficient: Main analysis only, 90% (two-sided); other analyses, 95% (two-sided)

7.2.5 Safety analysis

The following analyses regarding TEAEs will be performed on the “full analysis set” and “safety analysis set.”

TEAEs will be coded using MedDRA and summarized by SOC and PTs.

A subject with multiple events in the same SOC will be counted once for that SOC. A subject with multiple events with the same PT will be counted once for that PT.

7.2.5.1 Frequency tabulation of all TEAEs

7.2.5.2 Frequency tabulation of TEAEs for which the causal relationship with protocol treatment was “related”

7.2.5.3 Frequency tabulation of TEAEs for which the causal relationship with panitumumab was “related”

7.2.5.4 Frequency tabulation of all TEAEs by severity

7.2.5.5 Frequency tabulation of TEAEs by severity for which the causal relationship with protocol treatment was “related”

7.2.5.6 Frequency tabulation of TEAEs by severity for which the causal relationship with panitumumab was “related”

7.2.5.7 Frequency tabulation of TEAEs for action taken for protocol treatment was “discontinuation”

7.2.5.8 Frequency tabulation of TEAEs by severity for action taken for protocol treatment was “discontinuation”

7.2.5.9 Frequency tabulation of serious TEAEs

7.2.5.10 Frequency tabulation of serious TEAEs for which the causal relationship with protocol treatment was “related”

7.2.5.11 Frequency tabulation of serious TEAEs for which the causal relationship with panitumumab treatment was “related”

7.2.5.12 Frequency tabulation of non-serious TEAEs with > 5% incidence

- 7.2.5.13 Frequency tabulation of non-serious TEAEs with $> 5\%$ for which the causal relationship with protocol treatment was “related”
- 7.2.5.14 Frequency tabulation of non-serious TEAEs with $> 5\%$ for which the causal relationship with panitumumab was “related”
- 7.2.5.15 Frequency tabulation of TEAEs with \geq Grade 3
- 7.2.5.16 Frequency tabulation of TEAEs with \geq Grade 3 for which the causal relationship with protocol treatment was “related”
- 7.2.5.17 Frequency tabulation of TEAEs with \geq Grade 3 for which the causal relationship with panitumumab was “related”
- 7.2.5.18 The incidence rate of TEAEs with \geq Grade 3
- 7.2.5.19 The incidence rate of TEAEs with \geq Grade 3 for which the causal relationship with protocol treatment was “related”
- 7.2.5.20 The incidence rate of TEAEs with \geq Grade 3 for which the causal relationship with panitumumab was “related”

The following analyses will be performed on the “full analysis set” and “safety analysis set”:

The worst grade in each subject will be calculated. The incidence rate of TEAEs of Grade ≥ 3 and the 95% confidence intervals using Agresti-Coull methods will be calculated. Similarly, incidence rate and the 95% confidence interval of TEAEs will be calculated in the number of TEAE incidence with \geq Grade 3 as the numerator, and the TEAE collecting periods as the denominator. The 95% confidence intervals will be calculated using the following formula:

$$\text{The 95\% confidence intervals of incidence rate} = \text{incidence rate} \pm 1.96 \sqrt{\frac{\text{incidence rate}}{\text{TEAE collecting period}}}$$

Skin toxicity will be analyzed similarly as described above (7.2.5.1 to 7.2.5.20)

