4.1.3.4 Specified drug use surveillance results (all patients surveillance) in Japan

In the post- marketing surveillance conducted for a fixed period where all the patients treated were registered,⁸⁾ the median of treatment period (first day of treatment to the final day of treatment) for the 3,085 patients who were subject to safety evaluation was 113 days (range: 1 to 559 days), incidence of adverse reaction was 84.1% (25.8% \geq Grade 3), of which the panitumumab monotherapy group with 1,254 patients was 80.1% (19.7% \geq Grade 3), panitumumab + chemotherapy combination group with 1,831 patients was 86.9% (30.0% \geq Grade 3). The occurrence status of intensively investigated adverse reaction items are listed in Table 4.c.

Table 4.c Common adverse events in specified drug use surveillance in Japan

All patient surveillance	Panitumumab monotherapy group (n=1,254)				Panitumumab + chemotherapy combination group (n=1,831)			
	Any Grade		Grade 3 or higher		Any Grade		Grade 3 or higher	
Intensively investigated item	n	%	n	%	n	%	n	%
Skin & subcutaneous tissue disorders (SOC)	918	73.2	118	9.4	1446	79.0	274	15.0
Paronychia	272	21.7	33	2.6	459	25.1	99	5.4
Interstitial lung disease*	16	1.3	-	-	23	1.3	-	-
Infusion reaction	17	1.4	1	0.1	30	1.6	5	0.3
Hypomagnesaemia	257	20.5	61	4.9	263	14.4	62	3.4
Hypocalcaemia	59	4.7	16	1.3	77	4.2	26	1.4
Cardiac disorders (SOC)	2	0.2	0	0.0	5	0.3	1	0.1

SOC: System Organ Class

*: Interstitial pneumonia subcommittee criteria

CONFIDENTIAL

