4.1.4.2 Clinical study results for TAS-102

In Japan, after the phase I study in patients with solid tumors (J001 study) had been conducted, a phase II control study (J003 study) with OS as primary endpoint and PFS, DCR, etc. as secondary endpoints and the objective of assessing the superiority of TAS-102 group over placebo group in patients (number of safety assessed subjects: TAS-102 group 113, placebo group 57, efficacy assessed: TAS-102 group 112, placebo group 57) that have received previous treatment of 2 regimens including fluoropyrimidine agents, OXA, and IRI and with refractory or intolerant, unresectable, advanced/recurrent colorectal cancer was conducted.¹⁰⁾ TAS-102 was given 35 mg/m²/dose orally twice daily for 5 consecutive days, followed by 2 days of washout and after this was repeated twice, 14 days washout was implemented. As a result, OS prolongation was observed in the TAS-102 group compared to the placebo group. In the TAS-102 group, the OS median was 9.0 months, and by independent diagnostic imaging organization PFS median was 2.0 months, DCR was 43.8% (49/112 subjects). Common adverse events (occurrence 10%) noted in Japanese clinical study in 119* subjects are shown in Table 4.d.

*: 6 subjects who were given the same dosage and regimen as the J003 study in the Japanese phase I study (J001 study) were added to the 113 subjects of the Japanese phase II study (J003 study)

Table 4.d Common adverse events (occurrence 10%) noted in Japanese clinical study

Adverse event	Any Grades (n = 119)		Grade 3 or higher (n = 119)	
	n	%	n	%
Hematocrit decreased	34	28.6	1	0.8
Haemoglobin decreased	76	63.9	22	18.5
Lymphocyte count decreased	40	33.6	13	10.9
Neutrophil count decreased	87	73.1	61	51.3
Platelet count decreased	49	41.2	5	4.2
Red blood cell count decreased	38	31.9	1	0.8
White blood cell count decreased	91	76.5	36	30.3
Diarrhoea	40	33.6	6	5.0
Nausea	75	63.0	3	2.5
Stomatitis	18	15.1	-	-
Vomiting	34	28.6	3	2.5
Fatigue	63	52.9	7	5.9
Blood albumin decreased	13	10.9	-	-
Blood bilirubin increased	23	19.3	1	0.8
Weight decreased	14	11.8	-	-
Protein urine present	14	11.8	-	-
Decreased appetite	66	55.5	3	2.5

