The worst Grade in each subject will be calculated. The incidence rate of TEAE with \geq Grade 3 and the 95% confidence intervals using Agresti-Coull methods will be calculated. Similarly, incidence rate and the 95% confidence interval of TEAE will be calculated in the number of TEAE incidence with \geq Grade 3 as the numerator, and the TEAE collecting periods as the denominator.

The 95% confidence intervals is calculated by the formula following;

The 95% confidence intervals of incidence rate = incidence rate $\pm 1.96 \sqrt{\frac{\text{incidence rate}}{\text{during the TEAE collecting period}}}$

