6.3.3 Frequency tabulation of adverse events

The following analyses regarding treatment-emergent adverse events (TEAEs) will be performed on the “set of enrolled subjects who received at least one dose of protocol treatment and satisfied all of the enrollment criteria” and the “DLT evaluation set.”

TEAEs are adverse events that develop after initiation of protocol treatment.

Skin toxicity are events meeting the definitions of TEAEs in [Table 4.1](#).

TEAEs will be coded using MedDRA and summarized by SOC and PTs.

A subject with multiple events in the same SOC will be counted once for that SOC. A subject with multiple events with the same PT will be counted once for that PT.

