The worst grade in each subject will be calculated. The incidence rate of TEAEs of Grade ≥ 3 and the 95% confidence intervals using Agresti-Coull methods will be calculated. Similarly, incidence rate and the 95% confidence interval of TEAEs will be calculated in the number of TEAE incidence

with \geq Grade 3 as the numerator, and the TEAE collecting periods as the denominator. The 95% confidence intervals will be calculated using the following formula:

$$95\% \text{ confidence interval of incidence rate} = \text{incidence rate} \pm 1.96 \sqrt{\frac{\text{incidence rate}}{\text{TEAE collecting period}}}$$

Skin toxicity will be analyzed similarly as described above (6.3.3.1 to 6.3.3.20)

7. Statistical analysis of the phase II part of the study

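### The 95% interval for the person-time rate of Grade 3 or higher TEAEs collapses to zero width at no events and sets its upper limit too low at small counts

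*SAP*

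**What the plan says.** The SAP (version 4.0) plans two measures of Grade 3 or higher TEAEs, in 7.2.5.18–20 for phase II and 6.3.3.18–20 for phase I. Each is given overall, for events related to protocol treatment, and for events related to panitumumab.

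- **Proportion of subjects**, from the worst grade per subject, with Agresti-Coull limits.
- **Person-time rate**, where "incidence rate and the 95% confidence interval of TEAEs will be calculated in the number of TEAE incidence" of Grade 3 or higher, with "the TEAE collecting periods as the denominator". Its limits are the rate ± 1.96 times the square root of rate divided by collecting period.

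Protocol 13.3.4.1 has the same formula, beginning "The 95% confidence intervals of incidence rate = incidence rate". Both SAP sections extend these analyses to skin toxicity. None of the three places has a rule for zero events, truncation at zero, or an alternative for small counts.

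The SAP does not say whether the rate is pooled over all events or given by term. The introductions to 6.3.3 and 7.2.5 carry counting rules ("A subject with multiple events in the same SOC will be counted once for that SOC" and "A subject with multiple events with the same PT will be counted once for that PT"), but nothing ties them to the numerator of this rate.

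**The concern.** The formula is the normal-approximation (Wald) interval for a Poisson rate. It estimates the variance from the observed count, so with no events the estimated variance is zero and the interval has no width. With few events the interval is symmetric around a skewed quantity, so its lower end falls below zero and its upper end falls short.

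In a safety table the upper limit matters most, because it says how frequent a severe toxicity could still be. An interval of 0 to 0 reads as certainty that the event cannot occur. The error therefore runs in the unfavourable direction for safety reporting.

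**Working it through.** **Inputs.** The formula comes from SAP 6.3.3 and 7.2.5 and Protocol 13.3.4.1. The confidence level is 95% two-sided (SAP 7.2.4.5). Set sizes are about 6 subjects for phase I and 52 planned at the recommended dose (Protocol 6.1). Illustrative Grade 3 or higher rates come from Protocol Table 4.c ("Common adverse events in specified drug use surveillance in Japan") and Table 4.d ("Common adverse events (occurrence 10%) noted in Japanese clinical study"). The plan prints no result for this interval, so there is no figure to reproduce. The multiplier 1.96 is right for a two-sided 95% level.

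**Step 1: rewrite the formula.** With rate = k/T, √(rate/T) = √k/T, so the limits are (k ± 1.96√k)/T. For example, k = 3 gives 3 ± 1.96 × 1.732 = 3 ± 3.39.

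**Step 2: compare with exact Poisson limits.** The exact lower limit is χ²(0.025; 2k)/(2T), taken as 0 at k = 0. The exact upper limit is χ²(0.975; 2k+2)/(2T). The limits below are multiplied by T, so the comparison does not depend on T.

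| k | Planned formula | Exact Poisson | Planned upper ÷ exact upper |
|---|---|---|---|
| 0 | 0 to 0 | 0 to 3.69 | 0% |
| 1 | −0.96 to 2.96 | 0.03 to 5.57 | 53% |
| 2 | −0.77 to 4.77 | 0.24 to 7.22 | 66% |
| 3 | −0.39 to 6.39 | 0.62 to 8.77 | 73% |
| 10 | 3.80 to 16.20 | 4.80 to 18.39 | 88% |
| 50 | 36.14 to 63.86 | 37.11 to 65.92 | 97% |

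**Step 3: true coverage of the planned interval**, by summing Poisson probabilities over k.

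| Expected events | Coverage (nominal 95%) | Upper limit below the true rate (nominal 2.5%) |
|---|---|---|
| 1 | 63% | 37% |
| 2 | 86% | 14% |
| 3 | 80% | 20% |
| 4 | 91% | 9% |
| 5 | 87% | 12% |
| 10 | 93% | 7% |
| 20 | 95% | 4% |

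**Step 4: where small counts would arise.** This step assumes that each subject counts once per term and that rates equal those the protocol cites for other regimens. Counts are then binomial.

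| Set | Event, Grade 3 or higher | Rate | Expected | P(0) | P(3 or fewer) |
|---|---|---|---|---|---|
| Phase I, n = 6 | Skin disorder | 9.4% / 15.0% | 0.6 / 0.9 | 55% / 38% | over 99% |
| Phase I, n = 6 | Neutrophil decrease | 51.3% | 3.1 | 1% | 63% |
| Phase II, n = 52 | Nausea | 2.5% | 1.3 | 27% | 96% |
| Phase II, n = 52 | Platelet decrease | 4.2% | 2.2 | 11% | 83% |
| Phase II, n = 52 | Diarrhoea | 5.0% | 2.6 | 7% | 73% |
| Phase II, n = 52 | Paronychia | 2.6% / 5.4% | 1.4 / 2.8 | 25% / 6% | 95% / 69% |
| Phase II, n = 52 | Skin disorder, pooled | 9.4% / 15.0% | 4.9 / 7.8 | 0.6% or less | 27% / 4% |
| Phase II, n = 52 | Neutrophil decrease | 51.3% | 27 | about 0 | about 0 |

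**The case against.** The algebra is not in dispute. The case against concerns weight and remedy.

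- **The rate decides nothing.** The phase II safety endpoint is a percentage of subjects (Protocol 5.2.2), and phase I turns on DLT counts. This stands and limits the importance of the point.
- **A sound interval sits beside it.** For the proportion of subjects, Agresti-Coull gives an upper limit of 8.2% at 0/52 and 44% at 0/6. This stands as mitigation. It also means that the same 0/6 data would appear with an upper limit of 44% on one line and of zero on the next.
- **Poisson coverage overstates the loss if each subject counts once.** Under the binomial model of step 4, coverage is 90% for phase I neutrophil decrease, 89% for platelet decrease, 93% for diarrhoea, and 96% for phase II pooled skin disorder at 15.0%. This stands in part. Coverage is still 45% and 62% for phase I skin disorder, 73% for nausea, and 88% for phase II skin disorder at 9.4%.
- **Zero rows may never be printed.** If only observed terms are listed, a term without a Grade 3 or higher event may have no row. This is possible, since the SAP leaves the layout open. The negative lower limits and short upper limits at k = 1 to 3 would remain. Fixed rows, such as skin toxicity or panitumumab-related totals, could still show zero.
- **If only pooled phase II rates are reported, the defect is negligible there.** This is correct, but the phase I sets would still be affected.
- **Exact Poisson limits carry their own assumption.** Protocol 10.1.2 has events recorded in each course. If repeats within a subject count, events are clustered and exact Poisson limits are too narrow as well. This stands and is dealt with in the fix.

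**Conclusion.** The concern holds: the stated formula is wrong as written at low counts. It gives a zero-width interval at no events, impossible negative limits at one to three events, and an upper limit 27% to 47% below the exact one over that range. Coverage reaches about 93% only at around 10 expected events and 95% at around 20.

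The limits at each k follow from the formula alone. The coverage figures assume Poisson counts. How often small counts occur rests on rates borrowed from other regimens and on one count per subject per term. The phase I sets and rare single terms in phase II are exposed. Common or pooled phase II events are not. The primary analysis, the sample size and the Agresti-Coull intervals are unaffected. The formula should be corrected, but the point is confined to a descriptive safety table.

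**What to change.** In SAP 6.3.3.18–20, SAP 7.2.5.18–20 and Protocol 13.3.4.1, replace the formula with the exact Poisson interval:

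- lower limit χ²(0.025; 2k)/(2T), set to 0 when k = 0;
- upper limit χ²(0.975; 2k+2)/(2T).

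Keep Agresti-Coull for the proportion of subjects. In the same places, state whether the rate is pooled or by preferred term, and whether the once-per-subject rule governs the numerator. Only if a subject can contribute more than one event, use a subject-level robust or bootstrap variance instead.

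The cost is one line of wording in three places, one line of code, and the two definitions. No new data are needed. Intervals at low counts become wider and somewhat conservative, with coverage of about 98% to 99% at 1 to 5 expected events. Protocol 6.4 lists a change of safety evaluation method among the reasons for amendment, so the sponsor should decide whether the protocol wording needs one. Protocol 13.1 leaves detailed analysis methods to the SAP, so the SAP could carry the change, with the departure from Protocol 13.3.4.1 recorded.
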